2.1 Main Study

Aim 1: To test three putative brain mechanisms underlying increased caloric intake during nicotine withdrawal using an abstinence challenge paradigm (within-subject).

H1a: Brain signal will be associated with decreased working memory (WM) in the dorsolateral prefrontal cortex (DLPFC) and reduced suppression of activity in the posterior cingulate cortex (PCC).

H1b: There will be increased food cue-induced activity in the insula, anterior cingulate cortex (ACC), orbitofrontal cortex (OFC), and ventral striatum/nucleus accumbens (VS/NAC).

H1c: Increased food reinforcement choice-related activity in VS/NAC and ventromedial prefrontal cortex (vmPFC) will predict increased caloric intake (abstinence vs. smoking).

Aim 2: To evaluate the relative contribution of task-related brain signal (WM, Food Cue Response, Food Reinforcement/Choice) in prediction of nicotine abstinence-induced increase in caloric intake (within-subject).

H2a: Brain responses (H1a-c) will characterize abstinence challenge-induced change in caloric intake more accurately than clinical (age, sex, nicotine dependence, BMI), subjective (craving, withdrawal), and behavioral performance measures alone.

CONFIDENTIAL

This material is the property of the University of Pennsylvania. Do not disclose or use except as authorized in writing by the study sponsor

H2b: The relative contribution of domain-specific brain signal (WM, food cue reactivity and food reinforcement) to the prediction of abstinence challenge-induced increase in caloric intake will be evaluated (regression model).

EXPLORATORY AIM (between group): To provide a baseline comparison in food-related brain response between smokers and non-smokers.

This study will: (a) drive new insights about how the brain can constrain or promote the ability of smokers to prevent PCWG; and (b) lead to new theories and interventions that integrate neural and behavioral frameworks important for promoting behavior change. Support for our predictions would inform testing of novel approaches to prevent PCWG, such as computerized neurocognitive exercise training to increase DLPFC activity and shift activity away from reward sensitive brain networks.

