2.2 Overall Objectives - (Recruitment & Retention Pilot Study)

Aim 1: To evaluate the effects of information provision and incentives, alone and in combination, on study enrollment rates.

Hypothesis: Behavioral economic interventions will (Information provision & contingency management) will produce higher rates of enrollment compared to standard recruitment.

3 Study Design

General Design – Main Study

This is a within-subject cross-over neuroimaging investigation of 3 potential neural mechanisms of increased caloric intake during initial smoking cessation. Eighty smokers will be scanned on 2 occasions: (1) after 4 days of monitored abstinence (biochemically verified), and (2) after 4 days of smoking as usual (order counterbalanced) (**Figure 3**). In addition, 30 healthy non-smokers (matched for sex, age, and education) will complete one period of the study to serve as a baseline comparison group (see Exploratory Aim). As in prior studies, participants will have fasted overnight and be provided with a standard meal (BOOST® shake) when they arrive on testing days 4 and 32. Blood oxygen level dependent (BOLD) fMRI sessions will assess BOLD signal at rest and while performing tasks for food cue reactivity, food reinforcement (choice task), and working memory (N-back). Additional measures will be administered out of scanner (**Figure 3**). Caloric intake will be assessed on days 1-3 and 29-31 using a validated dietary recall procedure (days 4 and 32 are fMRI scan days and intake will be standardized). Caloric intake is the primary behavioral outcome. Task-induced BOLD signal change in hypothesized regions of interest and performance on the working memory, food cue, and food reinforcement tasks are the mechanistic variables.

CONFIDENTIAL

This material is the property of the University of Pennsylvania. Do not disclose or use except as authorized in writing by the study sponsor

Figure 3

Non-smoker Control Group (Baseline):

Day	-7	1 2 3 4
Activity	Intake	Period 1*

*non-smokers complete phase 1 with identical monitoring and assessment

**order of periods (abstinence vs smoking) is counter balanced

Smoker Group (within-subject):

Day	-7	1 2 3 4	5-28	29 30 31 32	1 Month Follow-up
Activity	Intake	Period 1	Washout	Period 2	Web-based Survey
State	Smoke	Abstain**	Smoke	Smoke	N/A

Behavioral Outcome:

- Caloric intake (dietary recall; Days 1-3* & Days 29-32)

Intermediate Outcomes: Day 4* & Day 32

- Food reward (out of scanner)
- Working memory (fMRI)

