5.5 Sample Size Determination

We plan to test hypotheses at a global 5% Type I error (alpha) for each family of hypotheses, and have chosen a completed sample (N=110) that will achieve at least 80% power using 2-sided tests. Our analysis of power was based on “effect size” (standardized difference). Effect sizes were calculated from our own preliminary data, from published data summaries, and from published estimates of effects (e.g., t statistics, coefficients, p-values) using validated summary methods. We have several hypotheses and more than one outcome measure for some (e.g., different brain regions). We will control error in a family-wise manner, adjusting alpha (Bonferroni Aims 1 and 2, Hochberg step-up procedure for Aim 3) for the number of tests within each hypothesis family. Bonferroni corrections will also be adjusted for the correlations among multiple outcomes.

Aim 1 includes 2 hypotheses (**H1a&b**) regarding treatment effects on neural responses, including 5 ROIs responding to food-related tasks. We test at $p<0.02$ because of the high correlation among ROIs within subjects ($\rho=0.54$). Estimates of effect size from our center data ($d=0.36$) indicate that we have 80% power to detect the effects. Aim 1 also tests hypothesis **H1c** for cessation effects. At the Bonferroni corrected threshold of $p=0.0167$, we have 80% power to detect small to medium effect sizes ($d=0.37$).

CONFIDENTIAL

This material is the property of the University of Pennsylvania. Do not disclose or use except as authorized in writing by the study sponsor

Aim 2 (H2a&b) essentially tests for mediation. The hypothesis that cessation increases food intake will be tested at 0.05, with power for effect sizes $\sim d=0.32$. For Aim 2b (ROIs predicting food intake), we expect a weaker correlation than H1a ($\rho=0.4$), and our adjusted threshold for significance is $p<0.01$. Expected effect sizes are approximately 0.5, and we expect 96% power to detect the effects.

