Aim 2 seeks to determine the additional explanatory value of brain signal over and above models using only clinical, subjective, and behavioral performance measures (**H2a**). The use of difference scores reduces a complex longitudinal analysis of mediation to an analysis of a single (non-repeated) measure. Our analyses will test for incremental change in R^2 when models incorporate brain data. We will also examine the correlations among our predictors and identify potential for collinearity via variance inflation. We will then construct models of $\Delta kCal$ admitting blocks of variables hierarchically, and testing for improvement in fit by Wald test, starting with clinical variables (age, sex, FTND, BMI), behavioral performance, and subjective responses to abstinence challenge (N-back, MNWS, QSU-B, food reinforcement task breakpoint). Finally, we will add the difference scores from imaging, and estimate overall improvement (**H2a**) in R^2 . At each stage, we will allow highly redundant variables to drop out if variance inflation factor (VIF) is greater than 5. We will then return to the clinical plus behavior model and test the addition of each brain domain separately, again using the incremental improvement in R^2 by domain (**H2b**). Finally, we will explore data reduction methods (Principle Component Regression, Partial Least Squares) for entering correlated imaging variables in order to minimize the confounding effects of correlated predictors.

Our Exploratory Aim is a between-group analysis to provide a baseline comparison in food-related brain response between smokers and non-smokers. The analysis will include 30 non-smokers who will take part in a single non-smoking phase of the study and will include each of the predictor measures in H1. The analysis will utilize one-way ANOVA methods, fitted with GEE regression (Gaussian family), with a 3-level design code representing non-smoker, smoker sated, and smoker abstaining (non-smokers will have only one entry per subject, smokers will have two). Non-smokers will be treated as the reference group. Comparisons of interest, non-smoker versus sated smoker, and non-smoker versus abstaining smoker, will be tested using the z-score corresponding to the regression coefficient. A small number of covariates may be included in the model to control error.

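### H2b asks for the relative contribution of three brain domains, but its only test adds each domain alone, so it cannot show that one contributes beyond the others

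*Combined protocol and SAP*

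**What the plan says.** Section 2.1 sets H2b as an evaluation, by regression, of "The relative contribution of domain-specific brain signal (WM, food cue reactivity and food reinforcement") in predicting the abstinence-induced increase in intake.

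Section 5.6 (Aim 2) builds the model in blocks: four clinical variables, then four behavioural and subjective ones, then all imaging difference scores together. That last step estimates overall improvement (H2a). For H2b the analyst will "return to the clinical plus behavior model and test the addition of each brain domain separately", "again using the incremental improvement in R^2 by domain". No H2b model holds two domains at once.

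Three other provisions in section 5.6 touch on collinearity: predictor correlations are examined, variables with a variance inflation factor (VIF) above 5 may drop out, and principal component or partial least squares regression is explored. The same section gives the cue and reinforcement tasks the same primary regions (VS and vmPFC).

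Section 5.5 puts the correlation among ROIs within subjects at 0.54 for Aim 1. It then says: "For Aim 2b (ROIs predicting food intake), we expect a weaker correlation than H1a", with 0.4 as the figure. For Aim 2b it gives a 0.01 threshold, effects of about 0.5 and 96% power. Section 3 fixes the within-subject sample: "Eighty smokers will be scanned on 2 occasions".

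**The concern.** A gain in R² from adding one domain to the base model is that domain's marginal association with the outcome. If two domains correlate, the variance they share is credited to both. A domain that merely tracks the active one then shows a gain and may pass its test. That answers whether the domain predicts intake beyond clinical and behavioural measures. It does not answer whether it contributes anything the other domains do not.

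H2b is the only analysis assigned to compare the domains. Section 2.1 says that support for the predictions would inform new interventions, with training to raise DLPFC activity as an example. A report that two or three domains contribute could be read as evidence for two or three separate pathways when the data support only one.

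**Working it through.** **Inputs.** From the documents: n = 80 smokers, 8 base covariates (4 + 4), two-sided alpha 0.01, correlations 0.4 and 0.54. Assumed: one active domain explaining R² = 0.15 or 0.25 of the change in intake, base covariates unrelated to outcome and brain signal, and a between-domain correlation ρ varied from 0.1 to 0.54.

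**The plan's own figure.** One-sample t test, d = 0.5, n = 80: noncentrality 0.5 × √80 = 4.47, critical value 2.640 on 79 df, power 0.964. The stated 96% reproduces. It is power for a single effect, with no adjustment for other domains.

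**One score per domain, separate addition.** A null domain correlated ρ with the active one has a large-sample gain g = ρ²R². With 80 − 1 − 8 = 71 residual df before entry and 70 after, the flagging rate is approximately the chance that a noncentral F(1, 70) with λ = 71g/(1 − g) exceeds its 1% critical value. Example: ρ = 0.4, R² = 0.15 gives g = 0.16 × 0.15 = 0.024, λ = 71 × 0.024/0.976 = 1.75, rate 9.9%.

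**Two ROIs per domain.** With equal correlation ρ throughout, the sums of two domains correlate 2ρ/(1 + ρ): 0.8/1.4 = 0.571 at 0.4 and 1.08/1.54 = 0.701 at 0.54. Squared, a null domain is credited with 0.33 or 0.49 of the active domain's R², against 0.16 or 0.29 for single scores. Flagging rates come from simulation with block F tests. At 0.1-0.3 between domains, the within-domain correlation is held at 0.54.

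| Between-domain ρ | One score, R² 0.15 | One score, R² 0.25 | Two ROIs, R² 0.15 | Two ROIs, R² 0.25 |
|---|---|---|---|---|
| 0.1 | 1.4% | 1.7% | 2% | 2% |
| 0.2 | 2.7% | 4.0% | 3% | 5% |
| 0.3 | 5.4% | 9.2% | 6% | 12% |
| 0.4 | 9.9% | 18.5% | 17% | 33% |
| 0.54 | 20.7% | 39.4% | 29% | 56% |

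With 2, 4 and 2 ROIs the highest rate is about 57%. Tested last-in, the null domain is flagged in about 1% of runs in every cell. With two active domains, each with marginal r = 0.447 (f² = 0.25, the plan's d = 0.5 in regression form), the separate-addition rates are 9% at ρ = 0.2 and 34% at 0.4. With a smaller marginal r of 0.243 the rate at 0.4 is 8%.

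**Would the VIF rule act?** For three equicorrelated scores, the R² of one on the other two is 2ρ²/(1 + ρ): 0.32/1.4 = 0.229 at 0.4 and 0.583/1.54 = 0.379 at 0.54. VIF = 1/(1 − R²) is 1.3 and 1.6, far below 5.

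**Ranking, one active domain.** The active domain has the largest gain about as often under either method: 94.5% separate against 94.2% last-in (one score, ρ 0.4, R² 0.15), 88.1% against 86.5% (two ROIs, same values), and 84.6% against 82.3% (2/4/2 ROIs, ρ 0.54, R² 0.25).

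**Power for the active domain.** One score, ρ 0.4, R² 0.15: separate λ = 71 × 0.15/0.85 = 12.5, power about 0.80; last-in λ = 69 × 0.15 × (1 − 0.229)/0.85 = 9.4, power about 0.66. Two ROIs, ρ 0.54, R² 0.15: 0.68 separate, 0.25 last-in (simulated).

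**The case against.** H2b does not say that contribution means unique contribution. Aim 2 is framed as value over clinical, subjective and behavioural measures, and separate addition tests that correctly; a domain correlated with the outcome is a predictor in that sense. This stands. A reader might infer that the H2b test is invalid, but the documents support only the narrower point that it cannot separate one domain from another.

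A reader might also infer that false attribution is frequent. The documents do not establish this. The 0.54 is a correlation among ROIs in food-related tasks, used to justify an alpha level. The 0.4 is one brief clause, read here as a correlation among predictors because the figure it is compared with is one. Neither is stated as a correlation between domains' difference scores, and at 0.1-0.2 the error is small.

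Nor does the overlap mean that the domains would be put in the wrong order: with one active domain, separate addition ranks it first as often as last-in does, or slightly more often. The plan also never sums the three gains, so double counting is not itself a reported result.

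The plan does acknowledge collinearity. But the VIF rule would not act at these correlations, the joint imaging model is tested only as a whole, and the component methods are exploratory. None gives a test of one domain given the others.

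**Conclusion.** The point holds in this form and should be fixed. H2b promises a comparison of domains and specifies only marginal gains, so shared variance is credited to every correlated domain at any non-zero correlation. The size is conditional: a domain with nothing of its own is flagged in about 1-5% of trials at between-domain correlations of 0.1-0.2, 5-12% at 0.3, and 10-57% if section 5.5's 0.4-0.54 apply between domains, against about 1% last-in. These figures assume one active domain, R² of 0.15-0.25, n = 80, alpha 0.01 and base covariates unrelated to brain signal; real covariates could absorb some of the shared variance. The ranking result was checked only with one active domain. The structural gap is certain; its practical size cannot be settled from the documents.

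**What to change.** In section 5.6 (H2b), keep the separate additions and label them marginal. Also fit the joint model, with base variables plus all three domains, and report each domain's last-in R² gain with its partial F or Wald test. Require that any statement that a domain contributes beyond the others rests on the last-in test.

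A Shapley or dominance split can be added as description. It should not replace the last-in test, because it averages over entry orders that include first-in: a null domain would still receive about 6-11% of the explained variance with single scores at correlations of 0.4-0.54, and 12-18% with two ROIs per domain.

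In section 5.5, state that the 96% power does not cover unique contribution. The cost is a few regressions on data already collected and an honest statement of lower power for the unique test (0.80 to 0.66, or 0.68 to 0.25, in the two cases above). A non-significant last-in result should therefore not be read as showing that a domain has no role.

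### Aim 2 measures the brain-data gain, and compares brain domains, by unadjusted in-sample R^2, which is positive by construction and favours whichever domain has more ROIs

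*Combined protocol and SAP*

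**What the plan says.** H2a in section 2.1 claims that brain responses will characterise the abstinence-induced change in caloric intake "more accurately than clinical (age, sex, nicotine dependence, BMI), subjective (craving, withdrawal), and behavioral performance measures alone". H2b asks about the relative contribution of three domains: working memory, food cue reactivity and food reinforcement.

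Section 5.6 turns both into R^2 comparisons on abstinent-minus-smoking difference scores. "Our analyses will test for incremental change in R^2 when models incorporate brain data". Blocks enter hierarchically, "testing for improvement in fit by Wald test", and the overall improvement in R^2 after adding imaging is the H2a estimate. For H2b the analysis goes back to the clinical and behavioural model and adds each domain by itself, "again using the incremental improvement in R^2 by domain". Variables with a variance inflation factor above 5 may drop out. Principal component regression and partial least squares are to be explored, for correlated predictors.

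The number of ROIs per domain differs between sections (working memory/cue/reinforcement):

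- Section 2.1, H1a-c: 2/4/2.
- Section 5.4.3 and the N-back paragraph that follows it: 2/4/2, with a partly different set of cue regions.
- Section 5.6, primary ROIs: 2/2/2, or 3/2/2 if left and right DLPFC enter separately.
- Section 5.6 with the secondary ROIs, which are given to both food tasks: 2/6/6 or 3/6/6.

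**The concern.** In-sample R^2 cannot fall when predictors are added, and it rises on average in proportion to how many are added, even if they are pure noise. Two things follow. The H2a estimate will be positive whether or not brain data carry information, so it cannot by itself support a statement about accuracy. And if domains contribute different numbers of ROIs, their raw increments are not on a common scale, although relative contribution is exactly what H2b asks about. The Wald test allows for the number of terms when it tests a block. It corrects neither the reported size of the gain nor the comparison of one domain's gain with another's. At stake is the mechanistic conclusion of Aim 2: which brain process best accounts for increased intake, and by how much.

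**Working it through.** **Inputs.** n = 80 smokers (section 3). Base model of 8 terms: age, sex, FTND, BMI, N-back, MNWS, QSU-B, food reinforcement breakpoint (section 5.6; one term each is an assumption). ROI correlation 0.54 (section 5.5), applied within a domain. One value per ROI and 80 complete cases (assumptions).

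**The plan's own figure.** Section 5.5 states 96% power for Aim 2b at an effect size of about 0.5 and p < 0.01. A two-sided one-sample t-test with n = 80 gives 96.4%; n = 110 gives 99.5%. The stated figure therefore rests on the 80 smokers and on a single one-degree-of-freedom test, not on a block of ROIs.

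**Expected raw gain from q noise predictors.** If the base model also explains nothing, the gain is q/(n-1). Given a base R^2 with p terms, it is (1 - R^2_base) x q/(n-1-p).

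| q | q/79 | base R^2 = 0.2: 0.8q/71 | base R^2 = 0.3: 0.7q/71 |
|---|---|---|---|
| 2 | 0.025 | 0.023 | 0.020 |
| 4 | 0.051 | 0.045 | 0.039 |
| 8 (all ROIs, 2/4/2) | 0.101 | 0.090 | 0.079 |

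With 60 complete cases the 8-ROI value is 8/59 = 0.136.

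**H2a by simulation** (10,000 null replicates, 8 ROIs). Mean raw gain 0.101, 95% range 0.029 to 0.21, positive in every run. The mean adjusted gain, using 1 - (1 - R^2)(n-1)/(n-1-p), was about 0.000; it exceeded zero in 44% of runs. The block test rejected at 0.05 in 4.6-5.3% of runs, so its size is correct.

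**H2b by simulation, no true effect.** Share of runs in which each domain has the largest gain, in the order working memory/cue/reinforcement:

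| ROIs | Raw R^2 | Adjusted R^2 |
|---|---|---|
| 2/4/2, domains uncorrelated | 20/61/19% | 34/34/32% |
| 2/4/2, between-domain correlation 0.2 | 19/62/19% | 32/35/33% |
| 2/2/2 | 33/33/34% | 33/33/34% |
| 3/2/2 | 48/26/26% | 33/33/34% |
| 2/6/6 (6,000 replicates) | 5/48/47% | 32/34/34% |
| 3/6/6 | 10/44/45% | 32/34/34% |

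**H2b with a real effect in one 2-ROI domain only** (one ROI, 2/4/2, domains uncorrelated):

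| Slope | Real domain first, raw / adjusted | Null 4-ROI domain first, raw / adjusted | Mean raw gain, real / 4-ROI null |
|---|---|---|---|
| 0.2 SD | 48% / 61% | 40% / 22% | 0.058 / 0.051 |
| 0.3 SD | 71% / 80% | 23% / 12% | 0.094 / 0.051 |

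**The case against.** **The Wald test is there, and Aim 2b uses p < 0.01.** This carries weight. Under the 2/4/2 null some domain passes 0.01 in only about 3% of runs, and among those the 4-ROI domain has the largest raw gain in about a third (33-36%). The 61-62% figure therefore mostly describes orderings of non-significant domains. But the plan does not make the domain comparison conditional on significance, and the H2a gain is reported on the raw scale in any case.

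**The direction is not settled.** Correct. A reader might infer that food cue is always favoured. That holds under sections 2.1 and 5.4.3 only. The primary ROIs in section 5.6 give no bias (2/2/2) or favour working memory (3/2/2). Nor do the documents support a layout in which cue alone has 6 ROIs: section 5.6 gives the secondary regions to both food tasks.

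**The plan never says it ranks domains.** Also correct. Ranking is an inference from the relative-contribution wording. But judging relative contribution by increments in R^2 still means comparing their sizes.

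**The order would usually be right anyway.** A reader might infer that raw R^2 gives the wrong order on average. It does not: at a slope of 0.2 SD the truly active domain still has the largest mean raw gain. With a strong effect (raw gain about 0.20) it comes first in 96% of runs by raw R^2 and 98% by adjusted R^2. The loss is confined to weak effects.

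**VIF pruning and data reduction may help.** Component methods can reduce the number of terms per domain, but the plan only explores them, and it aims both steps at collinearity. Neither corrects for block size.

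**Conclusion.** The concern holds in a limited form. The H2a estimate is inflated by about 10 points of R^2 when 8 ROIs carry no information at n = 80 (8 to 9 points if the base model explains 20-30%), and is positive by construction. The H2b comparison is biased toward domains with more ROIs whenever counts differ. Under 2/4/2 the 4-ROI domain leads in 61-62% of null runs against a fair 33%. When only a 2-ROI domain has a weak real effect, the null 4-ROI domain still leads in about 40%, against about 22% on adjusted R^2. With equal counts the between-domain bias disappears, but the H2a inflation remains.

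The type I error of the block tests is not affected. A reader might infer that H2a would be declared significant too often; the simulations show that it would not.

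These figures assume 8 base terms, 80 complete cases and one value per ROI. Section 5.6 also mentions activation extent; entering it beside percent signal change would double the imaging terms and the null gain.

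**What to change.** 1. Reconcile sections 2.1, 5.4.3 and 5.6 into one ROI list per domain. State whether left and right DLPFC enter separately, whether secondary ROIs enter the Aim 2 models, and that each ROI supplies one measure.
2. For H2b, compare domains on the change in adjusted or cross-validated R^2, with a confidence interval, or enter one pre-specified composite per domain so that every domain uses one degree of freedom. If cross-validating, use the same folds for all models and apply the VIF rule inside the folds.
3. For H2a, report the adjusted or cross-validated gain beside the Wald test, and base the accuracy statement on that gain. A positive adjusted gain alone is not evidence, since it occurs in about 44% of null runs, so the test and an interval should accompany it.

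The cost is SAP wording and a few lines of code, with no change to data collection or sample size. The reported R^2 gains will be smaller.

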5.2.4 Mandatory Abstinence Period for Smoking Group (~days 1-3 or 29-31)

Participants will be randomized with respect to the order of the study periods; one-half of participants will have their mandatory abstinence period on days 1-4 and one-half will have this period on days 29-32. On the evening prior to the mandatory abstinence period, participants will receive a 20-minute structured telephone counseling session from a trained smoking cessation counselor to prepare for the upcoming 4-day abstinence period. Quit strategies include identifying triggers and alternative behaviors to smoking, deep breathing, and stimulus control methods. The abstinence periods will be framed as "practice quit attempts" unaided by nicotine replacement therapy or other medication.

On study days 1-3 (period 1) and 29-31 (period 2), participants will come to the Center and complete measures that may include a CO reading, breath alcohol test (BrAC), and questionnaires (smoking behavior, urges, mood, withdrawal, eating). Please see measures

CONFIDENTIAL

This material is the property of the University of Pennsylvania. Do not disclose or use except as authorized in writing by the study sponsor

table for specific time points. To verify smoking abstinence participants must have a CO reading of <10ppm or >50% reduction from their intake CO value on day 1 (or 29) and a CO reading of <5ppm on days 2, 3, or 4 (or 30, 31 & 32). Participants that do not meet CO criteria, have a BrAC greater than 0.000, or a positive urine drug screen will be withdrawn from the study, unless the Principal Investigator permits the participant to reschedule the visit to a later date.

Day 1/Day 29 Back-up Scheduling: Some participants may choose to be scheduled as a back-up for another participant's Day 1 or Day 29 visit. This is done to ensure that this protocol is efficiently using the time that is reserved on the fMRI scanner days at Days 4 and 32. Participants who are scheduled as a back-up should prepare for their back-up Day1/Day 29 in the same way that they would prepare for a primary visit. On the day of the back-up, participants should arrive at the Center in the smoking state that they have been assigned to for their respective Day 1/Day 29. Upon arrival participants will go through the same visit check-in to verify eligibility for the visit.

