5.3.2 Mechanisms

Individualized Food (Pre-FCQ-S): In preparation for the food cue-induced craving task, participants will rate how appetizing they find pictures of food (e.g., cupcakes, fruits, vegetables) at the Intake Visit. Foods rated least appetizing (n=20) and foods rated most appetizing (n=20)

CONFIDENTIAL

This material is the property of the University of Pennsylvania. Do not disclose or use except as authorized in writing by the study sponsor

will be selected to create personalized food cue stimuli. This task will be administered during the baseline visit.

Preferred Snack Choice (Pre-RRVF): Participants will select either the salty (Lay's® Classic potato chips) or sweet (M&M's®) snack food as the snack to "work for" when completing the RRVF task over the remainder of the study. This determination will be made at the baseline visit.

Food Cue-Induced Craving (FCQ-S): Food cue-induced craving will be assessed using a personalized food cue exposure paradigm, whereby pictures of foods rated least appetizing (L, n=20), most appetizing (M, n=20), and a picture of a glass of water (W, n=20) will be presented to participants seated at a computer screen. Participants will be instructed to imagine tasting and eating the pictured food for as long as the image is presented. The images will be presented in six blocks. Each block consists of image presentation (10 images, 8 sec duration) and craving assessment. The M, L, and W food cues will be presented in one of two sequences (i.e., MWLMWL or LWMLWM) counterbalanced across participants. Before the task and after each block, participants will complete the state version of the Food Craving Questionnaire, Desire Subscale (FCQ-S). The 3 items (desire to eat, craving, urge to eat) will be tailored to ask about the M, L, and W images on a 5-point scale (strongly disagree to strongly agree). Personalized cues can maximize craving induction and produce greater increases in subjective craving and objective indices of cue reactivity than standard cues. Reactivity to palatable food images is associated with body mass and weight gain. The Food Cue-Induced Craving task will be administered at scan 1 (Day 4), and scan 2 (Day 32) Visits.

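### Exploratory Aim: non-smokers contribute first scans only, half of the smoker scans are second scans, and no scan-number term is prespecified

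*Combined protocol and SAP*

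**What the plan says.** Section 3 (General Design – Main Study) sets two different scan schedules. For smokers: "Eighty smokers will be scanned on 2 occasions", on days 4 and 32. The 30 non-smokers "will complete one period of the study to serve as a baseline comparison group", and the note to Figure 3 fixes which one: "non-smokers complete phase 1 with identical monitoring and assessment". Section 5.2.4 gives the order for smokers: "one-half of participants will have their mandatory abstinence period on days 1-4 and one-half will have this period on days 29-32".

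The analysis is in the Exploratory Aim paragraph of Section 5.6. It is a one-way model fitted by GEE "with a 3-level design code representing non-smoker, smoker sated, and smoker abstaining", with non-smokers as the reference, and "non-smokers will have only one entry per subject, smokers will have two". On testing: "Comparisons of interest, non-smoker versus sated smoker, and non-smoker versus abstaining smoker, will be tested using the z-score". The paragraph ends by leaving room for a few covariates, optional and unnamed, to reduce error. Scan number and period are not mentioned, and smokers are not restricted to their first scan.

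**The concern.** Counterbalancing protects comparisons in which every participant contributes both sessions. Here the reference group has no second session. If the response changes between a first and a second scan, through familiarity with the scanner, practice or habituation, that change enters both smoker means and not the non-smoker mean. A perfectly balanced order does not help, because the imbalance lies between groups.

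At stake is whether a difference between smokers and non-smokers can be read as one of smoking status. Besides matching, this comparison is the reason for enrolling the 30 non-smokers.

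**Working it through.** **Plan's own figure.** Section 5.5 gives no power, sample size or error rate for the Exploratory Aim, so there is nothing to reproduce.

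**Inputs from the documents.** 80 smokers with two scans each, in 1:1 order (40 abstain first, 40 smoke first). 30 non-smokers with one scan each, in Period 1. Both smoker scans enter the model.

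**Inputs assumed.** The second-minus-first-scan effect δ, in units of the SD of a single-scan response: 0 to 0.4. The correlation ρ between a smoker's two scans: 0.3 to 0.7. The correlation of 0.54 in Section 5.5 is between regions of interest, not between scans. It is used below only as a middle value.

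**Composition of the data**

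| Group | First scans | Second scans |
|---|---|---|
| Non-smoker | 30 | 0 |
| Smoker, sated | 40 | 40 |
| Smoker, abstaining | 40 | 40 |

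**Bias.** With δ common to both states, the expected smoker-state mean is μ(state) + (40/80)δ = μ(state) + δ/2. The expected non-smoker mean is μ(non-smoker). Each contrast is therefore biased by δ/2, both in the same direction. The abstaining-minus-sated difference carries δ/2 − δ/2 = 0.

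**Error rate.** SE = √(1/80 + 1/30) = √0.04583 = 0.214 SD. With no true difference, two-sided error = P(|Z + (δ/2)/SE| > 1.96).

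| Assumed δ (SD) | Bias δ/2 (SD) | Bias/SE | Two-sided error |
|---|---|---|---|
| 0 | 0 | 0 | 5.0% |
| 0.1 | 0.05 | 0.23 | 5.6% |
| 0.2 | 0.10 | 0.47 | 7.5% |
| 0.4 | 0.20 | 0.93 | 15.4% |

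**Simulation check.** The stated GEE was simulated with an exchangeable working correlation, ρ = 0.54 and 400 runs per scenario. At δ = 0.3 the formula gives a bias of 0.15 SD and an error of 10.8%; the simulation gave 0.14 SD and 9.5% for the sated contrast. With a scan-number term these fell to about 0.00 SD and 4.2%. At δ = 0 the simulated error was 6.2% without the term and 6.0% with it. The simulation error on a 5% rate is √(0.05 × 0.95/400) = 1.1 percentage points.

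**Cost of the term.** Smokers supply both scans in both orders, so δ is estimable from them, with variance 2(1 − ρ)/80. Half of the estimate is subtracted from each state mean, and with balanced order the two are uncorrelated. Hence SE = √(1/30 + [1 + (1 − ρ)/2]/80).

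| ρ | SE with term | Increase over 0.214 | Difference detectable with 80% power |
|---|---|---|---|
| 0.7 | 0.218 | 2% | 0.61 SD |
| 0.54 | 0.221 | 3% | 0.62 SD |
| 0.3 | 0.224 | 5% | 0.63 SD |

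Without the term the detectable difference is (1.96 + 0.84) × 0.214 = 0.60 SD.

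**Smokers' Period 1 scans only.** 40 per state against 30: SE = √(1/40 + 1/30) = 0.24 SD, detectable difference 0.68 SD, and no δ in either contrast.

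**The case against.** The strongest reply is that the session effect may be small or absent, and that parts of the design limit it.

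- Food pictures are rated, and the personalised set is chosen, before any scan. N-back is done at Baseline (Section 5.2.3), and abbreviated practice tasks precede each scan (Section 5.2.8). Table 2 does not restrict the picture rating or the Baseline N-back to smokers.
- N-back stimuli have alternate forms counterbalanced within subject (Table 1).
- The food-cue outcome compares most appetizing pictures with water and with least appetizing pictures from the same session (Section 5.4.3). A change common to all picture types cancels, leaving only differential habituation.
- The optional covariates in Section 5.6 could include scan number.
- The aim is exploratory, with no error-control claim attached.

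All of this stands, and it limits the point. It does not remove it. The choice task is contrasted with fixation (Section 5.4.3), so it has the least protection. Scanner familiarity still differs between groups. A permitted covariate is not a prespecified one.

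Four stronger readings are tempting, and the documents do not support them:

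- A reader might infer that day 4 is the non-smokers' first exposure to the tasks and pictures. The Baseline and practice procedures show otherwise; only the scanning session is new.
- A reader might infer that smokers will look less food-reactive than non-smokers. That needs a direction for δ, and none is given.
- A reader might infer that the aim cannot deliver its comparison. Over the assumed range the bias stays below one standard error.
- Section 5.3.2 says "Reactivity to palatable food images is associated with body mass and weight gain", and the groups are not matched on BMI, so a reader might infer that BMI must also be a fixed covariate. That is a choice of estimand. Section 1.1 links smoking status with weight, so BMI may lie on the pathway, and adjusting for it could remove part of the difference sought. The documents do not settle this.

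**Conclusion.** The point holds as a gap in prespecification with an inexpensive remedy. Both contrasts with non-smokers carry half of any repeat-scan effect, and the stated model has no term that separates it from smoking status. The imbalance itself follows from the design: 40 of 80 scans in each smoker state against 0 of 30.

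The size is wholly assumption-driven, from no bias at δ = 0 to 0.20 SD and 15.4% error at δ = 0.4 SD, with the sign unknown. It also assumes that δ is the same in both smoker states, and that the planned half-and-half split is achieved; loss of smokers after the first scan would lower the share of second scans and so the bias. The concern is greatest for the food choice task and smaller for N-back and the food-cue contrast. Aims 1 and 2 use within-smoker differences and are not affected.

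**What to change.** In the Exploratory Aim paragraph of Section 5.6, commit to a scan-number term in the GEE alongside the group code: first versus second scan, with all non-smokers coded as first. Both contrasts are then read at the first scan. No assumption is needed about how non-smokers would respond to a second scan.

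As a sensitivity check, repeat both contrasts with smokers' Period 1 scans only (about 40 per state). A single additive term would not fully remove the bias if the session effect differs between the sated and abstaining states; the Period 1 comparison covers that case. Because its SE is larger (0.24 SD), judge it on agreement of the estimates rather than on significance.

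The cost is SAP wording. Scan number follows from the study day, so no new data or visits are needed. The SE of the main contrasts rises by 2-5% for ρ from 0.7 to 0.3, and the detectable difference from 0.60 SD to 0.61-0.63 SD.
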